3.0 STUDY IMPLEMENTATION

3.1 STUDY DESIGN

3.1.1 *Overall Trial Design*

Patients with prostate cancer who have more than 15% risk of lymph node (as defined by the Partin tables) metastasis will be eligible for this study. The initial part of this trial (first 10 patients) explores the feasibility of using intensity modulated radiation therapy (IMRT) to deliver standard dose (4500 cGy) to the pelvic lymph nodes while dramatically reducing the volume of small bowel exposed. The prostate gland will receive the standard dose (7560 cGy). These first 10 patients will also undergo 3 to 5 CT simulations throughout the course of their therapy. On each simulation, the initial treatment plan will be re-run and the dose-volume data from target and normal tissues will then be re-analyzed. From this analysis we will be better able to determine the size of margins needed to account for organ motion and

changes such as varying amounts of gas in the bowel and fluid in the bladder. To the best of our knowledge, no such analyses have been published.

If the initial part of this trial is feasible, we will then proceed to a phase I dose escalation trial of radiation to the at-risk lymph nodes. The scientific objective is to determine what dose of external beam radiation is tolerable. Specifically, we will estimate the maximum tolerated dose (MTD) of external beam radiation to pelvic lymph nodes of interest in patients with prostate cancer.

Anatomic MRI and MR biological images will be obtained Tissue will be acquired from sites of interest, with biopsy locations precisely translated (co-registered) to an MR image of reference. Fiducial markers (gold seeds) may be left at the biopsy site(s) to direct future radiation therapy. The patient will undergo a standard CT simulation for radiation therapy treatment planning. The MR and CT images will be fused. Areas of image abnormality will undergo dose escalation as described below. The remainder of the prostate gland will receive standard dose (as per the Radiation Therapy Oncology Group (RTOG) 9406 study 7560 cGy in 180 cGy daily fractions.[1] Treatments will occur at the NCI, Department of Radiation Oncology on weekdays. There will be no treatments on weekends or holidays.

3.1.2 Dose Escalation

The first 10 patients will receive 4500c Gy to the prostate and pelvic nodes, followed by IMRT to prostate alone to 7560 cGy, which is standard dose to less volume than during whole pelvis radiation therapy.

The primary objective of this study to determine the MTD of radiation to pelvic lymph nodes (LNs) of interest (as determined by MRI) in patients with prostate cancer. based on evaluating acute toxicity. The study will be conducted with a dose-escalation design with 3 patients in each dose cohort.

Cohort	Prescription Dose to Lymph Node Regions	Max Dose to > 10 cc of Small Bowel	Max Dose Allowed Beyond Prostate + 7 mm
I	5040 cGy	5500cGy	7560 cGy
II	5400 cGy	5500cGy	7560 cGy
III	5900 cGy	5500cGy	7560 cGy

3.1.3 Criteria for Dose Escalation

Each dose cohort will accrue 3 patients. If there are no DLT in 3 patients then 3 patients will be accrued to the next dose level. If two or more patients experience a DLT then the MTD will be exceeded and the prior lower dose cohort will be considered the MTD. If a DLT occurs in one of three patients then an additional 3 patients will be accrued to that dose level. If fewer than 2 of 6 patients experience an acute DLT in the expanded cohort then patients will be accrued to the next dose cohort. If 2 or more of 6 patients experience a DLT then the MTD will be exceeded and the prior, lower dose cohort will be considered the MTD.

3.1.4 Definition of Dose Limiting Toxicity (DLT)

An acute DLT will be defined as RTOG grade 3 or greater, acute GI or GU toxicity (see appendix IIA) within 3 months after the completion of radiation. Thus, accrual to an escalated dose cohort may need to be delayed so that all 3 patients in the current cohort are followed for 2 months. Given that the volume of normal tissue irradiated to standard dose or higher will be substantially limited, late toxicity is less of a concern than acute toxicity.

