3.1.5 Definition of Maximum Tolerated Dose (MTD)

The primary objective is to estimate the MTD of external beam radiation that results in limiting acute toxicity. The MTD is defined as the dose level immediately below the dose level at which 2 or more in a cohort of either 3 or 6 patients experienced a DLT attributed to radiation therapy. If DLT does not occur at the highest dose level the protocol will be amended to escalate by 10% in cohorts of 3 patients each with the standard 3-6 dose escalation procedure.

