3.4.3 Radiation Treatment Phase

- Weekly AP (or PA) and lateral port films
- The following acute rectal toxicity endpoints will be measured
 - RTOG acute toxicity grading- GI & GU (Appendix IIA) weekly and at the completion of treatment

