5.3 TOXICITY CRITERIA

- Acute toxicities will be evaluated by the CTC, Version 3.0. (<http://ctep.info.nih.gov>).
- We will also utilize the RTOG acute and Late toxicity GI/ GU scales as in appendices II A & B.

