7.4 NCI-IRB AND CLINICAL DIRECTOR REPORTING

7.4.1 NCI-IRB and NCI CD Expedited Reporting of Unanticipated Problems and Deaths

The Protocol PI will report in the NIH Problem Form to the NCI-IRB and NCI Clinical Director:

- All deaths, except deaths due to progressive disease

- All Protocol Deviations
- All Unanticipated Problems
- All non-compliance

Reports must be received within 7 days of PI awareness via iRIS.

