7.5 DATA AND SAFETY MONITORING PLAN

7.5.1 Principal Investigator/Research Team

The clinical research team will meet on a regular basis weekly when patients are being actively treated on the trial to discuss each patient. Decisions about dose level enrollment and dose escalation if applicable will be made based on the toxicity data from prior patients.

All data will be collected in a timely manner and reviewed by the principal investigator or a lead associate investigator. Adverse events will be reported as required above. Any safety concerns, new information that might affect either the ethical and or scientific conduct of the trial, or protocol deviations will be immediately reported to the IRB using iRIS.

The principal investigator will review adverse event and response data on each patient to ensure safety and data accuracy. The principal investigator will personally conduct or supervise the investigation and provide appropriate delegation of responsibilities to other members of the research staff.

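### Radiation-attributed death or life-threatening acute toxicity outside GI/GU does not enter the DLT count, so the written rule still directs escalation

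*Combined protocol and SAP*

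**What the plan says.** The DLT is defined in 3.1.4: "An acute DLT will be defined as RTOG grade 3 or greater, acute GI or GU toxicity", with a window of 3 months after radiation ends.

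Section 3.1.3 uses only that count. "If there are no DLT in 3 patients then 3 patients will be accrued to the next dose level", and "If a DLT occurs in one of three patients then an additional 3 patients will be accrued to that dose level". Fewer than 2 DLTs in 6 leads to escalation; 2 or more in 3 or 6 means the MTD has been exceeded. Section 3.1.5 places the MTD just below the level at which "2 or more in a cohort of either 3 or 6 patients experienced a DLT attributed to radiation therapy".

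Other sections touch on wider toxicity:

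- 5.3: "Acute toxicities will be evaluated by the CTC, Version 3.0". No CTC grade is tied to a dosing decision.
- 3.4.3 schedules "RTOG acute toxicity grading- GI & GU (Appendix IIA) weekly and at the completion of treatment". The toxicity scales listed for follow-up in 3.4.4 are also RTOG GI and GU.
- 7.5.1 provides weekly team review and immediate reporting of safety concerns to the IRB, and says: "Decisions about dose level enrollment and dose escalation if applicable will be made based on the toxicity data from prior patients".
- 7.4.1 requires a report within 7 days for "All deaths, except deaths due to progressive disease".
- 7.3.1 has adverse events reported up to 30 days after the last dose.

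**The concern.** The aim in 3.1.1 is to find a tolerable dose, and tolerability is not confined to two organ systems. Under the written rule, a death or life-threatening acute event attributed to radiation but arising elsewhere contributes nothing to the count. With no GI/GU DLT, the cohort is 0 of 3 and the next dose level opens. The MTD comes from the same count, so the reported MTD would not reflect the event either.

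Two things are at stake: the safety of the next 3 patients, and what the reported MTD means. Such an event at 5900 cGy, the top level, would also leave standing the provision in 3.1.5 to amend the protocol and escalate by a further 10% (5900 × 1.10 = 6490 cGy).

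**Working it through.** **1. Reproduce the plan's figures.** With DLT probability p per patient, the rule in 3.1.3 gives

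P(escalate) = (1−p)³ + 3p(1−p)² × (1−p)³ = (1−p)³ + 3p(1−p)⁵.

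| p | Computed | Stated in 5.4 |
|---|---|---|
| 0.1 | 0.906 | 0.91 |
| 0.3 | 0.494 | 0.49 |
| 0.5 | 0.172 | 0.17 |
| 0.7 | 0.032 | 0.03 |

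The stated figures are correct for whatever event is counted as a DLT.

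**2. What the rule does with an uncounted event.** Take 3 patients at 5400 cGy: one with an RTOG grade 3 GI event, one with a radiation-attributed non-GI/GU death, one with neither. As written this is 1 of 3, so the cohort expands; if the next 3 have no DLT it is 1 of 6 and 5900 cGy opens. If the death counted, it would be 2 of 3 and the MTD would be 5040 cGy.

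**3. Size.** The documents give no rate for such events, so both inputs are assumptions: g = GI/GU DLT risk (0.10 or 0.20) and q = risk of an uncounted event (0.01 or 0.02), taken as independent. If both count, p = 1 − (1−g)(1−q).

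| g | q | p | P(escalate) | Change from q = 0 |
|---|---|---|---|---|
| 0.10 | 0 | 0.100 | 0.906 | – |
| 0.10 | 0.01 | 0.109 | 0.891 | −1.5 points |
| 0.10 | 0.02 | 0.118 | 0.875 | −3.1 points |
| 0.20 | 0 | 0.200 | 0.709 | – |
| 0.20 | 0.01 | 0.208 | 0.691 | −1.7 points |
| 0.20 | 0.02 | 0.216 | 0.674 | −3.5 points |

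**4. Counting a death is not enough by itself.** One death in 3 patients, with the other two clean, only expands the cohort. Escalation still follows if the next 3 are clean: (1−p)³ = 0.9³ = 0.729 at p = 0.10, and 0.8³ = 0.512 at p = 0.20.

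**5. Effect on expansion.** P(expand to 6) = 3p(1−p)². For q = 0, 0.01 and 0.02 this is 24.3%, 26.0% and 27.5% at g = 0.10, and 38.4%, 39.1% and 39.8% at g = 0.20. The cap in 5.4 is 19 = 10 + 3 × 3, which leaves no place for an expansion if all three cohorts open.

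**6. Collection.** If the last dose in 7.3.1 means the last radiation fraction, general adverse event reporting stops at 30 days while the DLT window runs to 3 months. A non-GI/GU event in the second or third month need not be recorded as an adverse event.

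**The case against.** The GI/GU focus is a reasoned choice. Section 1.2.1 names small-bowel tolerance as the barrier to nodal dose escalation. Only the nodal dose rises across cohorts in 3.1.2; the small-bowel and prostate-margin limits stay fixed. Fatigue is the only common acute effect outside GI/GU in 6.3, and most other non-GI/GU harms listed there are long-term. The documents identify no particular severe acute non-GI/GU effect. All of this stands, and it is why the point is small.

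A reader might infer that the plan would escalate blindly past a death. The documents do not support that. Section 7.5.1 bases dose decisions on toxicity data, not DLTs alone, and has safety concerns reported to the IRB at once. Deaths not due to progression are reported within 7 days, and 3.1.4 allows a delay before the next cohort opens. What remains is that none of these provisions sets a trigger or a hold, or changes the MTD. A reader might also infer that fatal GI/GU toxicity is excluded; it arguably counts, because grade 3 or greater has no upper limit.

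A third tempting reading is that the effect is large. The chance that a cohort has at least one uncounted event and still escalates is (1−g)³[1−(1−q)³] + 3g(1−g)⁵[1−(1−q)⁶]. For q = 0.01 and 0.02 that is 3.2% and 6.3% at g = 0.10, and 2.7% and 5.3% at g = 0.20. This is not the effect of a change: many of those cohorts would escalate under an amended rule too, because one event only expands the cohort. Higher values of q give larger differences, but nothing in the documents supports them.

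**Conclusion.** The concern holds as a gap in the written rule. A radiation-attributed non-GI/GU death or life-threatening acute event does not enter the escalation or MTD count, and the existing oversight permits a hold without requiring one.

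The numerical effect is small: about 1.5 to 3.5 points on P(escalate), given independence, q of 1% to 2% and g of 10% to 20%, all of them assumptions. The case for acting rests on the seriousness of the event and the low cost of the change. The probabilities in 5.4 are not wrong because of this.

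It might be inferred that every grade 3 event in any organ should count. The documents do not support going that far. All patients receive hormone therapy, so attributing lesser systemic events would be hard. The CBC is listed only before treatment (2.2.2, 3.4.1) and PSA is the only laboratory test at follow-up (3.4.4), so laboratory-graded events would be seen unevenly. This is an item to consider, not a major flaw.

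**What to change.** Three short additions:

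- **3.1.4:** *Any death, or CTC v3.0 grade 4 or greater non-GI/GU acute toxicity, attributed to radiation therapy and occurring from the start of radiation to 3 months after its completion, is also a DLT.* Keep the RTOG scale for GI/GU. Grade 4 is meant to capture life-threatening events, and attribution follows 3.1.5.
- **3.1.3:** *A death attributed to radiation therapy within this window pauses accrual until the IRB has reviewed it and approved resumption.* Step 4 of the working shows why the count alone is too weak.
- **7.3.1:** extend adverse event collection from 30 days to 3 months after radiation, using the existing 2, 4, 8 and 12 week visits and no added laboratory tests.

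Do not adopt a blanket CTC grade 3 trigger, even with an exception for fatigue.

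Costs: slightly more cohort expansion (under 1.5 points at g = 0.20 and about 3 points at g = 0.10 when q = 0.02), under a cap that already cannot absorb one if all three cohorts open; some attribution difficulty because of hormone therapy; and a possible accrual delay. A single non-GI/GU event would still not set the MTD by itself, but it would enter the count.

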- The prostate will be treated to 7560 cGy in 180 cGy daily fractions (42 fractions.)
 - The maximum dose 7 mm or more beyond the prostate will be no more than 7560 cGy.
 - No More than 25% percent of the rectal volume shall receive more than 70 Gy.
 - The maximum dose to the prostatic urethra, bladder, and rectum will be limited to 78 Gy.
- For the first 25 fractions, in addition to the prostate, the high risk lymph node bearing regions of the pelvis will also be treated with IMRT to a total dose of 4500 cGy.
- The maximum dose 7 mm beyond the lymph node regions will be no more than 5040 cGy.
 - No more than 10cc of the small bowel will receive more than 55 Gy.
- There will be daily localization of the prostate and fiducial markers using portal imaging.
- All patients will receive 5 further CT simulation studies during the course of therapy
 - We will again run the initial plan on these subsequent CT simulations.
 - We will compare the dosimetry parameters above across the CT simulations
 - This analysis will allow us to determine what margins are truly appropriate to provide adequate coverage of the target volumes
- All patients will receive neoadjuvant, concurrent, and adjuvant hormone therapy.

Treatment

After the First 10 Patients (Phase I Dose Escalation)

- The MRI of the prostate and pelvis will be registered to the treatment planning CT scan.
- The prostate will be treated to 7560 cGy in 180 cGy daily fractions (42 fractions.)
- The maximum dose 7 mm or more beyond the prostate will be no more than 100% of the prescription dose of 7560 cGy.
 - No More than 25% percent of the rectal volume shall receive more than 70 Gy.
 - The maximum dose to the urethra, rectum and bladder will be limited to 78 Gy.
- In addition to the prostate, the high risk lymph node bearing regions of the pelvis will also be treated with IMRT in 180 cGy daily fractions. Total dose will be determined by dose cohort.
- The maximum dose 7 mm beyond the lymph node regions will be no more than 5040 cGy.
 - No more than 10cc of the small bowel will receive more than 55 Gy.
- There will be daily localization of the prostate and fiducial markers using portal imaging.
- All patients will receive neoadjuvant, concurrent, and adjuvant hormone therapy.

Follow Up:

- Toxicity
- MRI to evaluate for changes in imaging.
- Genomic and proteomic study of biopsied tissue

Table of Contents

1. Introduction	
1.1 Study Objectives.....	5
1.2 Background and Rationale.....	5

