3.2.3 Radiation Therapy

3.2.3.1 Prostate

3.2.3.1.1 Treatment planning

Planning target volume (PTV) 1 will be defined as the great vessels and a concentric 2.5 cm margin. Specifically, the aorta 2 cm proximal to the bifurcation, the common, internal, and external iliac vessels will be contoured. This margin may be edited at the treating physician's discretion (e.g. to meet normal tissue dose constraints). PTV 1 will be treated to a total dose of 4500 cGy in 180 cGy daily fractions in the first 10 patients. Thereafter, dose escalations will occur as per protocol. Daily dose will remain 180c Gy per day.

PTV 2 will be defined as the prostate and a 3 mm uniform margin. PTV 2 will be treated to a total dose of 75.6 Gy in 180 cGy daily fractions.

If indicated, the seminal vesicles may also be contoured and treated. When indicated, the seminal vesicles may be treated to 5400 cGy in 180 cGy.

3.2.3.1.2 Summary Of Dose Constraints:

Highest Priority:

- PTV2 will be defined as the prostate with a 3 mm uniform margin. The prescription dose to PTV2 will be 7560 cGy in 180 cGy daily fractions. No volume 4 mm beyond PTV2 will be allowed to receive a dose beyond 100% of the prescription dose.
- Less than 25% of the rectal volume will be irradiated to 70 Gy.
- The maximum dose to 10cc or more of small bowel will be no more than 5500 cGy.

Secondary Priority:

- PTV1 will be taken to full dose as per protocol.
- No more than 40% of the bladder will receive more than 6500 cGy.

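### The DLT definition gives no start other than the completion of radiation; read literally, it leaves out toxicity during the 8.4-week course in which all of the escalated nodal dose is given

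*Combined protocol and SAP*

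**What the plan says.** The only definition of a DLT is in Section 3.1.4: "RTOG grade 3 or greater, acute GI or GU toxicity (see appendix IIA) within 3 months after the completion of radiation". The next sentence deals with timing between cohorts: "accrual to an escalated dose cohort may need to be delayed so that all 3 patients in the current cohort are followed for 2 months". Sections 3.1.3 (escalation criteria) and 3.1.5 (MTD) use the term without adding a window.

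Section 3.4.3 requires, during radiation, "RTOG acute toxicity grading- GI & GU (Appendix IIA) weekly and at the completion of treatment". This is the scale that the DLT definition cites. Section 3.4.4 then schedules acute-effect visits 2, 4, 8 and 12 weeks after therapy ends, with late-effect visits from 6 months. Section 7.5.1 bases escalation on toxicity in earlier patients and does not say over which period.

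On the course itself, the Schema states: "The prostate will be treated to 7560 cGy in 180 cGy daily fractions (42 fractions". Section 3.1.1 adds: "Treatments will occur at the NCI, Department of Radiation Oncology on weekdays". The escalated factor is the column headed "Prescription Dose to Lymph Node Regions" in Section 3.1.2: 5040, 5400 and 5900 cGy in cohorts I to III. Section 3.2.3.1.1 fixes the fraction size: "Daily dose will remain 180c Gy per day".

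Section 3.8 lists reasons for leaving the study, including refusal of further treatment. It attaches no rule on DLT status, evaluability or replacement.

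**The concern.** The second primary objective is the MTD of nodal radiation, judged on acute toxicity. A window that opens when radiation is complete opens after the last of the nodal dose has been given. Section 6.3 describes the common acute effects as temporary, so a grade 3 reaction could appear and settle before the window opens. It would then be on file as a weekly grade without entering the DLT count.

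In cohorts of 3 or 6, one patient can change the decision. If one DLT among three patients is missed, the result is 0 of 3 and the trial escalates instead of expanding. If one of two DLTs among six is missed, the result is 1 of 6 and the trial escalates instead of declaring the MTD exceeded. Missed events can only push towards escalation and towards an MTD that is too high, which concerns patient safety as well as bias.

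A second gap concerns early stopping. For a patient who stops radiation early, perhaps because of toxicity, the text does not say whether completion means the planned course or the last fraction given, or how that patient enters the count of 3 or 6.

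**Working it through.** **Inputs.** Total prostate dose 7560 cGy in 42 fractions (Schema); treatment on weekdays (Section 3.1.1); 180 cGy per fraction (Section 3.2.3.1.1); nodal doses 5040, 5400 and 5900 cGy (Section 3.1.2); escalation rule (Section 3.1.3); stated escalation probabilities 0.91, 0.49, 0.17 and 0.03 at DLT rates 0.1, 0.3, 0.5 and 0.7 (Section 5.4).

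**Step 1: what the literal window leaves out.**
- Course length: 7560/180 = 42 fractions; 42/5 = 8.4 weeks, ignoring holidays.
- Nodal fractions: 5040/180 = 28; 5400/180 = 30; 5900/180 = 32.8.
- All three are below 42, so in any sequence the whole nodal dose falls before the full course is complete.

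**Step 2: reproduce the plan's own figures.** Let p be the DLT probability and q = 1 − p. Under Section 3.1.3 the trial escalates after 0 of 3, or after 1 of 3 followed by 0 of 3:

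P(escalate) = q³ + 3pq² × q³

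- p = 0.1: 0.7290 + 0.2430 × 0.7290 = 0.906 (stated 0.91)
- p = 0.3: 0.3430 + 0.4410 × 0.3430 = 0.494 (stated 0.49)
- p = 0.5: 0.1250 + 0.3750 × 0.1250 = 0.172 (stated 0.17)
- p = 0.7: 0.0270 + 0.1890 × 0.0270 = 0.032 (stated 0.03)

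All four agree. The three-patient rule in the Précis (escalate if fewer than 2 of 3) would give 0.972, 0.784, 0.500 and 0.216, so Section 3.1.3 is the rule behind the stated figures.

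**Step 3: apply the literal window.** Let f be the share of patients with a DLT whose grade 3 or worse toxicity occurs only on treatment. The rate that counts is p(1 − f), which replaces p in the formula. The documents give no value for f, so a range is shown.

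| f (assumed) | Rate counted, true p = 0.30 | P(escalate) | Rate counted, true p = 0.50 | P(escalate) |
|---|---|---|---|---|
| 0% | 0.300 | 0.49 | 0.500 | 0.17 |
| 25% | 0.225 | 0.65 | 0.375 | 0.35 |
| 50% | 0.150 | 0.81 | 0.250 | 0.60 |
| 75% | 0.075 | 0.94 | 0.125 | 0.86 |

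Worked example, p = 0.50 and f = 50%: the counted rate is 0.25, q = 0.75, and P = 0.4219 + 0.4219 × 0.4219 = 0.600.

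The 0% row also describes the inclusive reading, in which on-treatment events count and the figures in Section 5.4 stand.

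**The case against.** The strongest reply is that the phrase sets only an outer limit, separating acute from late toxicity. The text gives this real support. The rest of Section 3.1.4 deals with how long to follow a cohort and with late toxicity. Section 3.4.4 draws a similar line between the 12-week and 6-month visits. Section 3.4.3 collects the RTOG acute grade weekly and treats it as an endpoint. Section 7.5.1 has the team meet weekly during treatment and does not bar on-treatment data from escalation decisions. This reading is plausible, so a reader should not infer that the plan deliberately excludes on-treatment events. What remains is that no section adopts the inclusive reading, and the acute visits at 2 to 12 weeks fit the literal one just as well. Appendix IIA, which the definition cites, is not in the available text, so whether it states a grading period cannot be checked.

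A reader might also infer that a patient who stops early is counted as free of DLT. The documents do not say that. Completion could mean the last fraction given, and Section 3.8 is silent on the count. The supportable point is that the handling is undefined.

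Finally, a reader might infer that the cohorts are observed unequally because prostate-only treatment would last (42 − 28)/5 = 2.8, (42 − 30)/5 = 2.4 and (42 − 32.8)/5 = 1.8 weeks after the nodal dose. This assumes that nodes are treated first. The Schema says so only for the feasibility part ("For the first 25 fractions, in addition to the prostate"); for the dose-escalation part it does not place the nodal fractions within the 42. The unequal gap is not part of the finding.

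**Conclusion.** The point holds as a defect in the definition of the primary endpoint. Its only time anchor is the completion of radiation. Applied as written, it omits the 8.4 weeks in which all of the escalated dose is given, and it does not say how a patient who stops early is counted. Two teams following the text could score the same patient differently and make different escalation decisions.

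The size depends on two conditions: that the literal reading is applied, and the assumed on-treatment share. With shares of 25% to 75%, the probability of escalating rises from 0.49 to between 0.65 and 0.94 at a true rate of 0.30, and from 0.17 to between 0.35 and 0.86 at 0.50. With a share of zero, or under the outer-limit reading, there is no inflation. The figures therefore show what the wording puts at risk; they do not show that DLTs were or will be undercounted by any given amount. The direction is certain under the literal reading: towards escalation.

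It should be corrected before the DLT rule is relied on.

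**What to change.** Reconcile Section 3.1.4 with Section 3.4.3. State that the DLT observation period runs from the first fraction to 3 months after the last fraction actually delivered, and that the weekly on-treatment RTOG grades count. State how a patient who stops radiation early is classified for the count of 3 or 6, including whether that patient is evaluable or replaced; the sponsor should choose and write down that classification. Section 3.1.4 also pairs a 3-month window with a 2-month wait before escalation, and these need to be reconciled in the same edit.

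The cost is a sentence or two. The weekly grades are already collected, so no new assessments are needed. If on-treatment events were always meant to count, the change only records that intent. If they were not, more events will count and escalation may stop earlier.

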3.4.4 Post Active Treatment Evaluation (follow- up)

- Upon completion of therapy, patients will be evaluated at 2, 4, 8 and 12 weeks for acute effects of radiation therapy. Patients will be evaluated at 6, 9, 12, 18 and every 6 months afterward for late effects until 36 months.
- Follow-up visits will include:
 - A directed history and physical examination,
 - PSA evaluation
 - Rectal toxicity assessment including:
 - RTOG acute toxicity grading- GI & GU (Appendix IIA)
 - RTOG Late toxicity grading- GI & GU (Appendix IIB)
 - EPIC (Appendix IIIC).
 - AUA Symptom Score (Appendix IV)
 - Sexual Health Inventory For Men (Appendix V)
- Follow-up MRI may be obtained after completion of therapy to better delineate the time of course of signal change after radiation therapy.

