5.4 STATISTICAL SECTION

This is a phase I study to determine the maximum tolerated dose (MTD) with MRI-guided radiation dose escalation to regions of interest within the prostate gland. The dose cohorts and MTD are defined in Section 3.1.1. With this design, the probabilities of dose escalation are 0.91, 0.49, 0.17, and 0.03 if the probabilities of a DLT are 0.1, 0.3, 0.5, and 0.7, respectively

Secondary analysis includes evaluating the frequency of late term toxicities. We will tabulate the frequency of late term toxicities. All secondary analyses will be reported as exploratory.

The maximum number of patients accrued to this trial will be 19 patients. We anticipate accruing these patients within 2 years.

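### The DLT window runs to 3 months after radiation, but the accrual hold derived from it is only 2 months, so the next dose level can open before the window closes

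*Combined protocol and SAP*

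**What the plan says.** Section 3.1.4 defines the dose-limiting event as RTOG grade 3 or worse "acute GI or GU toxicity (see appendix IIA) within 3 months after the completion of radiation". The following sentence, presented as a consequence, says that opening an escalated cohort may have to wait "so that all 3 patients in the current cohort are followed for 2 months". It does not say when the 2 months begin.

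The surrounding sections read as follows.

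- Section 3.1.3 escalates after zero DLTs among three patients and adds three patients after one DLT. "If fewer than 2 of 6 patients experience an acute DLT in the expanded cohort", the next level opens. No follow-up time is attached to any of these counts.
- Section 3.1.5 defines the MTD from the same DLT counts.
- Section 3.4.4 schedules the acute assessments: after therapy ends, "patients will be evaluated at 2, 4, 8 and 12 weeks for acute effects of radiation therapy".
- Section 7.5.1 states: "Decisions about dose level enrollment and dose escalation if applicable will be made based on the toxicity data from prior patients". It sets no minimum follow-up.
- Section 5.4 says that "the probabilities of dose escalation are 0.91, 0.49, 0.17, and 0.03" for DLT probabilities of 0.1, 0.3, 0.5 and 0.7. It caps enrolment at 19 and adds: "We anticipate accruing these patients within 2 years".

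**The concern.** A 2-month hold does not follow from a 3-month window. A team that applies Section 3.1.4 literally can enrol at the next level while the last patient of the current cohort still has the week-12 visit and about a month of DLT observation to come. A DLT first seen in that month counts toward the MTD under Section 3.1.5, yet the escalation that it should have informed has already been made. Sections 3.1.3, 3.1.5 and 7.5.1 do not say what happens then.

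The same sentence leaves three further gaps. The hold has no start point. It is worded as a possibility rather than a requirement. It names three patients, although Section 3.1.3 also escalates from an expanded cohort of six. Two teams could open a cohort at different times, hold different DLT counts for the same level, and both claim to have followed the protocol. The MTD is the primary objective of the phase I part.

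**Working it through.** **Timing.** At 30.44 days per month, 2 months = 2 × 30.44 / 7 = 8.7 weeks and 3 months = 3 × 30.44 / 7 = 13.0 weeks. Counted from completion of radiation, the hold ends 12 − 8.7 = 3.3 weeks before the last acute visit and about 4.3 weeks before the window closes. Counted from the first fraction, 42 fractions at 5 per week take 8.4 weeks, so the hold would end 8.7 − 8.4 = 0.3 week, about 2 days, after treatment.

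**The plan's own figures.** With every DLT known at the decision, the Section 3.1.3 rule gives

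P(escalate) = (1−p)³ + 3p(1−p)² × (1−p)³ = (1−p)³ + 3p(1−p)⁵.

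At p = 0.1, 0.3, 0.5 and 0.7 this is 0.906, 0.494, 0.172 and 0.032. All four figures in Section 5.4 reproduce, so they rest on complete ascertainment.

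**Deciding at 2 months.** Let f be the share of DLTs first seen in month 3. The documents give no onset times, so f is an assumption: 20%, range 10–30%. Let q = p(1−f) be the probability that a DLT is seen by 2 months. Trio 1 is taken as fully observed by the time trio 2 is judged.

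- *Only the last patient of each trio is at 2 months.* A = (1−p)²(1−q) is the chance that a trio shows no DLT. B = 2p(1−p)² + q(1−p)² is the chance that trio 1 shows one DLT and has no other. P = A + B × A. At p = 0.3, f = 0.2, q = 0.24: A = 0.49 × 0.76 = 0.3724; B = 0.294 + 0.1176 = 0.4116; P = 0.3724 + 0.1533 = 0.526.
- *A whole trio finishes together.* P = (1−q)³ + 3q(1−p)²(1−q)³ = 0.4390 + 0.3528 × 0.4390 = 0.594.
- *Ceiling, all six at exactly 2 months.* P = (1−q)³ + 3q(1−q)⁵ = 0.622.

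| P(escalate), f = 20% (10–30%) | p = 0.3 | p = 0.5 |
|---|---|---|
| All DLTs known | 0.49 | 0.17 |
| Last patient of each trio at 2 months | 0.53 (0.51–0.54) | 0.20 (0.19–0.22) |
| Whole trio at 2 months | 0.59 (0.54–0.65) | 0.28 (0.22–0.35) |
| Ceiling | 0.62 (0.56–0.69) | 0.31 (0.23–0.40) |

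**Escalated, then a late DLT in the cohort that justified it** (p = 0.3, f = 0.2, so pf = 0.06).

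- Last patient only: 0.49 × 0.06 + 0.4116 × (0.49 × 0.06) = 0.0294 + 0.0121 = 0.042. Two or more DLTs in that cohort arise only through the second term: 0.012.
- Whole trio: (0.4390 − 0.3430) × (1 + 0.3528) = 0.130. Two or more DLTs: (3 × 0.06² × 0.7 + 0.06³) + 0.3528 × 0.0960 = 0.0078 + 0.0339 = 0.042.

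**Which case is likely.** Nineteen patients in 24 months, spaced evenly, are 24 / 19 = 1.26 months apart. When patient 3 is at 2.0 months, patients 2 and 1 are at about 3.3 and 4.5 months. Now allow for two pauses, each the treatment time of 1.93 months plus the 2-month hold, or 3.93 months. That leaves 24 − 7.86 = 16.1 months over 16 intervals, or 1.0 month each, which puts patients 2 and 1 at about 3.0 and 4.0 months. Either way only the last patient is clearly incomplete. Faster accrual within a cohort moves toward the whole-trio figures.

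**The case against.** The strongest reply concerns actual exposure. Section 3.2.3.1.1 keeps the daily dose at 180 cGy, so a higher nodal dose means more fractions. A Cohort II patient passes the Cohort I nodal dose only after 5040 / 180 = 28 fractions (5.6 weeks), and a Cohort III patient passes the Cohort II dose only after 5400 / 180 = 30 fractions (6.0 weeks). The uncovered gap is about 4.3 weeks. Even a patient who starts radiation on the day the hold ends has not passed the prior level's nodal dose when the window closes. Section 3.2.3.3 also requires at least 2 months of neoadjuvant hormone therapy before radiation, although some of it may precede entry. This is correct, and it limits early over-exposure when the hold is counted from completion. It does not repair the rule. Patients can still be enrolled and begin treatment at the next level before the count is final, and no section provides a mid-course check at which a late DLT would change their treatment.

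It can also be said that Section 3.1.3 is the operative rule and that, since DLTs are defined over 3 months, a count of zero is not established earlier. That is a sensible reading, but Section 3.1.4 is the only place that says how long to wait, and it says 2 months.

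Some of the criticism of the supporting points stands. The first-fraction reading is weak, because the preceding sentence and Section 3.4.4 both count from completion. Extending the hold to the second trio is the natural reading, although it is unwritten. The gap between week 12 and week 13.0 is small. The value of f is an assumption, and if f = 0 the probabilities do not change.

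**Conclusion.** The concern holds, and the escalation rule must be corrected. As written, Section 3.1.4 lets a dose level be judged and the next one opened about 4.3 weeks before the DLT window of the last patient closes, and no other section prevents it. This conclusion rests on the wording and needs no assumption about when DLTs occur.

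The numerical effect does depend on an assumption and is probably modest. At the planned pace, with 20% of DLTs first seen in month 3, the chance of escalating from a level with a true 30% DLT rate rises by about 0.03 (0.526 − 0.494). The chance that a level is escalated and then proves to have two or more DLTs is about 1.2%. If patients within a cohort finish together, the rise is about 0.10 (0.594 − 0.494) and that chance is 4.2%. The ceiling figures are a bound, not an expectation.

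**What to change.** In Section 3.1.4:

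- Reconcile the 2-month and 3-month intervals with each other and with the visit schedule in Section 3.4.4, saying whether the week-12 visit or the full 3 months (about week 13.0) closes the DLT window. Which interval is right is for the sponsor to decide.
- State the event from which the hold is counted.
- State, as a requirement, that the escalation decision is made only when every patient in the current cohort (three, or six if expanded) has completed the stated DLT window or has had a DLT.

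Once hold and window match, no separate rule is needed for a DLT found after escalation, and the probabilities in Section 5.4 apply as stated.

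The cost is a few sentences and a cross-reference to Section 3.4.4, with no new visits. If the longer interval is kept, each of the two escalation steps may take up to about 4.3 weeks longer.
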